## Specific Aims

The objective of the proposed research is to employ the Replicating Effective Programs (REP) implementation framework and Community-Based Participatory Research (CBPR) principles to develop and test a computer-assisted cognitive behavioral therapy (CBT) for rural persons with depression for group-based delivery in rural church settings, while gathering preliminary information on intervention implementation, including acceptability and feasibility. Almost 20% of Americans meet diagnostic criteria for depression during their lifetime and it is projected to be the second leading cause of disability by 2020. Rural Americans experience depression at rates similar to their urban counterparts, and the comorbidity of depression and anxiety disorders suggest that as many as 50% of rural residents with depression may also experience anxiety. Recent research shows higher mortality rates among rural Americans in midlife compared to urban peers, in part due to higher rates of suicide and substance use. Despite demonstrated need, rural residents are significantly less likely to receive mental health treatment than urban counterparts. This unacceptable gap between efficacy research and real world practice in rural areas necessitates the integration of EBPs to usual, preferred care settings. Bridging this gap and increasing rural Americans' access to EBPs for depression requires consideration of availability, accessibility, and acceptability of services. The lack of mental health professionals, transportation challenges, and high costs are substantial barriers to care in rural communities, yet even when treatment is available, many rural persons choose not to seek care. Stigma, shared beliefs and values such as independence and self-reliance, mistrust of formal providers, and explanations of depressive symptoms incongruent with urban-based treatment models, influence rural Americans' attitudes toward help-seeking and have led to a preference for informal systems of care. The proposed research seeks to increase rural populations' access to EBPs for depression by adapting group CBT to be context-specific and for delivery in a non-stigmatizing, accessible setting. As Americans seek help from clergy at high rates, and rural Americans report higher levels of religious involvement than urban residents, the church setting provides a logical, promising option for delivering EBPs for depression in rural communities. CBT has been shown to effectively treat depression among diverse populations, across a variety of treatment settings, and when delivered by lay providers and in their usual care settings. Limited research testing CBT in rural communities suggest promising results; though all studies include adaptations, yet rarely assess fidelity to standard CBT. These studies suggest the importance of incorporating consumer perceptions of mental illness and treatment and identifying delivery settings that overcome cost and stigma-related obstacles; however, very little attention has been paid to collaborating with rural stakeholders to build interventions for sustainability.

The proposed intervention, ***Raising Our Spirits Together (ROST)***, will utilize a community-based participatory approach to adapt and package group CBT for depression for delivery in the rural church setting. ROST will include three components: 1) computer-assisted delivery of core CBT content (e.g., psychoeducation; behavioral activation; cognitive restructuring); 2) multi-media training and manuals for group leaders facilitating sessions (e.g, guide exercises; discuss vignettes and case studies; review homework); and 3) participant workbooks.

### Specific Aims of the proposal, guided by the REP implementation framework and CBPR, are:

#### 1) Intervention Development and Testing.

- a. Part 1 (see HUM00130956). Utilize a community-based approach to adapt group CBT for depression for the rural context and for delivery in the church setting.
- b. Part 2 (see HUM00173088). Conduct an open pilot test of the adapted intervention. The intervention will be further refined and finalized based on experiences with the open pilot. Adaptation and refinement, guided by perceptions of community stakeholders, provide the best chance at successful integration of an adapted EBP (ROST) into the church setting, maximizing acceptability and sustainability.
- c. **Part 3 (focus of current IRB application): Conduct a pilot randomized controlled trial (Phase I/II RCT) of ROST to:**
  - i. **Assess the intervention's preliminary effect on depression among persons living in rural communities**
  - ii. **Explore the relationship between potential mechanisms of change and expected outcomes.**

**2) Implementation.** Explore ROST acceptability and feasibility using a mixed method process evaluation to assess multiple stakeholder and partner site perceptions of and experiences with ROST. This will provide insight to implementation facilitators and barriers.

The proposed research has the potential to make a large impact on the lives of individuals living with depression and other mental disorders in rural settings by making CBT available in a preferred community setting and reducing significant barriers related to limited availability of providers, cost, and stigma. Utilizing an established implementation framework, integrated with community-based participatory research principles, to guide intervention adaption and evaluation allows for the development of an intervention with the best chance for acceptability, feasibility, and sustainability in underserved rural communities.

## Research Plan

### Background

**Significance.** Depression is a significant public health concern, projected to be the leading cause of disease burden by 2020. Almost 20% of Americans experience depression during their lifetime. When untreated, the disorder has devastating effects on work, family and social life. Despite high prevalence, only one-third of persons with depression seek treatment. Rural Americans experience depression at rates similar to urban peers; yet, rural residents are significantly less likely to receive mental health care. Despite decades of efficacy research, rural residents are unlikely to receive EBPs for depression.

Rural residents face substantial barriers to care, the most significant of which may be the shortage of mental health providers. 75% of rural counties lack a practicing psychiatrist and 55% lack a practicing social worker or psychologist. This shortage is exacerbated by access challenges, including high poverty and unemployment rates, high proportions of uninsured or underinsured persons, and travel burden.

Even when mental health treatment is available, rural Americans often choose not to seek care. Values of self-reliance and independence contribute to beliefs that psychiatric distress is a weakness, leading to shame and stigma. Lack of anonymity also deters help seeking, as limited social networks make obtaining care without being noticed difficult. Further, rural residents often perceive cultural dissimilarities between themselves and providers. These factors suggest formal mental health services are not acceptable to many rural residents. In fact, rural persons prefer informal systems of care (e.g., clergy, friends, and family).

*Increasing rural populations' access to and utilization of EBPs for depression requires context-specific adaptations that decrease known barriers. As mental health providers are scarce in rural areas, it is imperative to explore non-mental health settings that could offer treatment.* Americans seek help for emotional issues from clergy at high rates. Rural residents tend to be more religious than urban residents and churches remain the heart of many rural communities. Among a sample of rural southerners with untreated depression, 68% of whites and 93% of people of color stated they would seek mental health services if they were available at church. Offering EBPs for depression at no cost in a non-stigmatizing, accessible church setting is likely to reduce barriers impacting rural populations' treatment utilization. Receiving EBPs from a preferred informal provider in an acceptable setting may increase openness to seeking traditional care if needed in the future. Therefore, the church setting is a promising option for disseminating evidence-based mental health treatment.

Literature suggests church-based interventions for health promotion have potential to reduce disparities; though underscore the importance of utilizing CBPR principles for successful recruitment, participation, and sustainability. Limited work has examined church-based mental health interventions, and only one identified study tested a church-based depression group. Results were promising; however the intervention included a very narrow population (female African American caregivers); did not make adaptations for church setting, did not report collaboration with stakeholders, and did not assess factors related to intervention implementation.

Cognitive behavioral therapy (CBT) is effective for treating depression in group and individual formats, among diverse populations, across a variety of treatment settings and when delivered by non-mental health professionals in their usual care settings. Growing evidence suggests the effectiveness of technology-assisted CBT. Though technology-assisted CBT is helpful for increasing access to care, it has better results when paired with professional support. Therefore, it is likely that clergy, who have strong interpersonal skills, could be trained to facilitate technology-assisted group CBT in church settings. Limited research testing the

effect CBT for depression and anxiety delivered in rural areas suggest promising results, however, all studies include intervention adaptations, yet very few assess fidelity. Further, very little attention has been paid to collaborating with rural stakeholders to build interventions for acceptability and sustainability.

*The state of knowledge reveals the need for more rigorous effectiveness and implementation research on CBT for depression delivered in rural community settings.* The proposed research utilizes the Replicating Effective Programs (REP) implementation framework and CBPR to adapt and pilot test CBT for depression for integration within rural church settings, while exploring acceptability and feasibility. Treating depression often improves anxiety, a secondary outcome. Potential mechanisms of change (Figure 1, below) will be explored.

The proposed intervention, ***Raising Our Spirits Together (ROST)***, will utilize a community-based approach to adapt and package group CBT for depression for the rural context and delivery in the church setting. ROST will include three central components: 1) computer-assisted delivery of core CBT content (behavioral activation; cognitive restructuring); 2) multimedia training and manuals for group leaders; and 3) participant workbooks. This format is consistent with self-help programming commonly offered in churches (e.g., Purpose-driven Life; 40 million copies sold), but distinct due to its use of EBP. Given the existing infrastructure for delivering small group programs, the church setting is well suited for deploying group CBT.

## **Research Strategy**

The primary aim of this research is to develop and test a computer-assisted group-based cognitive behavioral therapy for depression, entitled Raising Our Spirits Together (ROST), that will be delivered within church settings in rural Hillsdale County, Michigan. The primary aim is comprised of three distinct phases, which are described in detail below:

Part 1: Intervention Development. This aspect of the project is associated with a separate IRB application: HUM00130956.

Part 2: Open Pilot of ROST. This aspect of the project is associated with a separate IRB application: HUM00173088.

Part 3: Randomized Controlled Trial (Phase I/II RCT) of ROST compared to and Enhanced Control Condition. This aspect of the project is the focus of the current IRB application and the following protocol is specific to the Phase I/II RCT.

The secondary aim of this research is to gather preliminary information on ROST implementation.

### **Aim 1: Develop and test a computer-assisted group-based cognitive behavioral therapy (CBT) for depression (Raising Our Spirits Together (ROST))**

### **Part 3: Randomized Controlled Trial (Phase I/II RCT) of ROST compared to and Enhanced Control Condition**

**Purpose.** The purpose of this project is to conduct a Phase I/II RCT of ROST, evaluating its preliminary effect on depression relative to an enhanced control condition (ECC; see below).

**Intervention Arm: Raising Our Spirits Together (ROST).** ROST is an 8-session, computer-assisted, group-based cognitive behavioral therapy (CBT) for depression that is intentionally designed for delivery by clergy in rural church settings or remotely via secure videoconference software available via the University of Michigan. ROST uses a combination of video-based educational content, text-based educational content, and a character-driven storyline to introduce core CBT concepts, including psychoeducation, behavioral activation, cognitive restructuring, and problem solving. The ROST intervention package also includes a participant workbook and intervention manual for group leaders.

### **Session by Session Overview**

Session 1 – Psychoeducation and Introduction

Session 2 – Behavioral Activation

Session 3 – Behavioral Activation

Session 4 – Cognitive Restructuring

Session 5 – Cognitive Restructuring

Session 6 – Faulty Beliefs

Session 7 – Problem Solving/Overcoming Setbacks

Session 8 – Program Overview and Relapse Prevention

ROST was intentionally designed to deliver CBT in a way that is robust, yet widely accessible. Therefore, we paid close attention to the reading level of our content, used a combination of text, audio, and graphics to introduce core concepts in order address multiple learning needs, and streamlined interactive exercises and homework/action plan exercises to be more intuitive and less cumbersome/academically-oriented while focusing on the same central concepts. Our community-engaged intervention development work led to the selection and integration of images, quotes, vignettes, and examples that are likely to be most relevant and relatable for this setting. For example, each session begins with a quote from scripture that connects to the core CBT content being taught that day. We also identify potential activities for behavioral activation in Session 2 and 3 that can be done for free and within the rural context that lacks resources and infrastructure.

Additionally, aspects of rural culture, related to self-reliance and independence, led to the inclusion of “I cannot ask for help” as an example of a faulty belief we explore in Session 6. Another central adaptation related to our use of character driven content that compliments and reinforces core CBT session content. The character-driven, video-based content was designed to enhance participant engagement in ROST. The character also shows how she used CBT in her life, which provides a concrete example to participants as they apply CBT concepts in their own lives.

Please note that documents presenting comprehensive content for every ROST session are provided as part of the IRB application. Images of the computer-assisted platform and character-driven content have been submitted as supplemental materials in the IRB application as well.

Participants randomized to ROST will complete weekly sessions that last for approximately ninety minutes (8 sessions total). ROST will either be delivered in-person at one of our partner churches, or virtually, via secure, web-based videoconferencing software available through the University of Michigan. The pastor will facilitate in-person and virtual pilot groups. Participants randomized to ROST will receive \$10 for each ROST session they attend to compensate them for travel and parking expenses.

**Clinical Backup.** We recognize ROST leaders will need clinical backup. [name] and [name], who are both licensed clinical social workers, will provide clinical backup and will be available for group leaders via phone or video conference consultation if a study participant’s condition worsens or suicidality is present. Contact between clinical backup, group leaders, and study participants will be tracked to inform ROST feasibility. Study team members providing clinical back up will complete a half-day training that includes an overview of ROST, their role, and relevant study procedures related to risk assessment and safety planning.

**Control Arm: Enhanced Control Condition (ECC).** An enhanced control condition (ECC) is an appropriate comparison condition for the RCT, given the limited treatment access in the rural target community. When participants screen positive for depression, there is an ethical obligation to provide resources and referrals. ECC participants will receive a self-help workbook that provides psychoeducation, as well as local resource guides and appropriate referrals. Ongoing risk assessment of ECC participants will occur at post-treatment (PT) and follow-up (FU) assessment timepoints. The suicide risk protocol (see Protection of Human Participants) will be followed if suicidal ideation is present.

**Participants and Recruitment.**

**Enrollment and Participants.** We expect to recruit and enroll 128 men and women *who live within Hillsdale, Lenawee, Calhoun, Jackson or Branch County, Michigan* to participate in this Phase I/II RCT of ROST.

Hillsdale, Lenawee, Calhoun, Jackson and Branch counties are all rural counties within Michigan that are a designated mental health provider shortage areas. The poverty and unemployment rates in these three counties are above the national average. We expect to screen 177 persons, with 80% meeting screening criteria, providing informed consent, and agreeing to BL interviews (N=160). Of those 160 participants, we expect 80% who complete BL interviews will meet eligibility criteria (N=128). We expect 80% of those 128 participants to attend randomization (N=103). Of those attending randomization, we expect 82% (N=84; ROST=42; ECC=42) to participate in their assigned condition and be included in the RCT (Power analysis described below).

**Recruitment.** Community-based recruitment, via both in-person and virtual/web-based strategies will be used. These strategies will include putting up flyers in community locations (e.g., libraries, coffee shops, grocery stores, restaurants, schools, churches, social service agencies), airing an ad on the local radio station, and posting recruitment materials on relevant community websites and social media sites. We will put study flyers up at our church study sites and the pastors may directly refer potential participants to the research project. Study team contact information will be on all recruitment materials. Interested potential participants may contact us directly. If potential participants are referred to the project by a social service provider or clergy and are interested in participating, they will have the option to complete a contact form so a research associate from the study team can contact them at a later time. The contact form will ask participants to provide a phone number, additional contact persons, and an email address, and to identify their preferred method of contact. Confidentiality is emphasized.

In-person research will follow many safety protocols due to COVID-19. In-person recruitment will only be outdoors. Before beginning conversation with participants, an abbreviated health screen will be administered. Specifically, interested individuals will be asked whether, in the past 24 hours, they have had: 1) a fever, 2) a cough, 3) nasal congestion, 4) loss of taste/smell, 5) close contact with anyone who tested positive for COVID-19 or is positive for COVID-19. If any interested individual endorses two or more symptoms, study team members will not engage with them at that time. They will be provided with recruitment materials and can reach out by phone or email at a later time.

Plans for social distancing include conducting recruitment activities outdoors only. At these outdoor settings (e.g., food bank, farmers market), a study team member will set up a booth that allows for at least six feet of distance between staff and individuals interested in learning about the study. Staff will bring signage to communicate expectations for social distancing (i.e., keeping at least 6 feet apart) as well as signage that can be placed on the ground in front of the booth to provide a visual of 6 feet distance necessary to maintain between individuals.

Staff will complete the ResponiBlue screening daily and wear masks when engaged in outdoor recruitment. Individuals interested in the study will be encouraged to wear masks and extra masks will be available to interested individuals who approach the booth without a mask. Hand sanitizer and cleaning wipes will be kept at the booth at all times. Staff will wipe down the booth and use hand sanitizer after interacting with each individual interested in the study. Single use pens will be available at the booth for interested individuals to use. Interested individuals can complete a contact form with their contact information so that a study team member can reach out to them about the study. Contact forms can be dropped into a plastic box. The contact forms will be removed from the box at the end of the day and put into an envelope. The box will be sanitized with cleaning wipes.

Research associates will contact potential participants who voluntarily complete a contact form by phone or email and briefly describe the study. If the potential participant remains interested, the research associate will schedule a phone screen to determine initial eligibility.

All recruitment materials for the open pilot will avoid stigmatizing terms and include diverse images in terms of race/ethnicity, gender, and age, promoting inclusiveness.

**Inclusion.** In order to participate in this study, persons must: 1) currently live in Hillsdale, Branch, Jackson, Calhoun, or Lenawee County, Michigan. All persons residing in these counties may participate, regardless of religious beliefs; however, like Alcoholics Anonymous, participants will be informed of and must accept that non-denominational Christian-based quotes and images are included; 2) screen positive for at least mild depressive symptoms on the Patient Health Questionnaire-9 (PHQ-9 $\geq$ 5); and 3) not currently receive Cognitive Behavioral Therapy (CBT) treatment. Persons taking medication for depression may participate. Medication use will be monitored. Participants will be advised to continue taking any psychiatric medication according to their clinician/physician's instructions; though medication stabilization will not be required for inclusion. [name] research in non-mental health settings suggest medication stabilization is not feasible given the likelihood of multiple prescribing providers. Depressive disorder diagnoses will be assessed via structured interview (MINI v 7), but is not required for inclusion. Depressive disorder diagnosis will be considered in analyses. This increases access for underserved persons with a range of symptoms; helps fill groups faster; and is most generalizable to real world implementation.

**Exclusion.** Persons will not be eligible for the study if they 1) are non-English speaking; 2) currently receive regular CBT for depression (>1 time per month); 3) ever completed a course of CBT ( $\geq$ 8 sessions); 4) have a psychotic disorder; 5) currently use opiates cocaine; 6) have cognitive impairment ( $\geq$ 2 incorrect items on the 6-item mini mental status exam); or 7) have prominent suicidal/homicidal ideation with imminent risk. Indicators for imminent risk will be assessed by the interviewer. Subjects with significant suicide/self-harm or homicide risk must be excluded on ethical grounds and will receive appropriate resources and referrals (see Protection of Human Participants).

**Randomization.** Persons meeting eligibility criteria will be randomized to ROST or the ECC. Randomization will occur in replicated blocks across conditions. This procedure will repeat until 7, six-member ROST groups and 7, six-member ECC groups are assembled. If participant flow prevents timely assembly, smaller groups will be considered to avoid extended delays.

**STUDY SITES:** There will be two study sites for the RCT, located in Hillsdale County. The study sites are our partner churches, Trinity Lutheran Church and Jonesville First Presbyterian Church. ROST will either be delivered in-person at one of our partner churches, or virtually, via secure, web-based videoconferencing software available through the University of Michigan. The pastors will facilitate in-person and virtual ROST groups.

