**Data Analyses.** Primary outcome measures for assessing ROST's preliminary effect on depression relative to ECC are the PHQ-9 and BDI. We expect to enroll 128 subjects, 84 of whom we anticipate will participate in the study after randomization to condition. A sample of 84 subjects who participate in their study condition after randomization should provide power of .8 to find a significant (at 2-tailed  $p < .05$ ) comparative effect size for intervention change of  $d=.8$  or above, which is in ranges found in CBT meta-analyses. Analyses will adjust for BL scores to increase precision and maximize power. Other BL covariates will be examined for association with outcome variables. Those accounting for change in the estimated treatment effect will be retained in final analyses to optimize power and precision. As ROST is group-based, with participants blocked on time of screening prior to randomization, individuals' observations cannot be assumed independent. Due to lack of independence, mixed linear (multilevel) growth modeling will be used to test for the preliminary effect of ROST relative to ECC on outcome variables. Mechanisms of change will be explored by adding change on variables targeted by the intervention (thoughts; stigma) as time-varying covariates to multilevel models predicting change in depression over time. To explore the possibility that treatment effects may differ for those presenting with low v high religiosity and moderate v severe depression, baseline religiosity and baseline depression severity will be examined as potential moderators. Although this RCT is not powered for mediation or moderation tests, effect sizes from these analyses will inform future fully powered research to test mechanisms of change. Analyses will be "intent-to-treat," as all subjects undergoing randomization will be included, and will use multiple imputation methods and pattern mixture modeling to handle data missing at follow-up and sensitivity analyses to examine the influence of missingness on findings.

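### The screening forecast does not multiply out, and the stated power of .8 neither follows from its printed inputs nor refers to the intent-to-treat population that will be analysed

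*Combined protocol and SAP*

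**What the plan says.** Under Participants and Recruitment (Enrollment and Participants), the forecast begins: "We expect to screen 177 persons, with 80% meeting screening criteria, providing informed consent, and agreeing to BL interviews (N=160". It then expects 80% of the 160 to be eligible, which is 128. Next: "We expect 80% of those 128 participants to attend randomization (N=103". Of these, 82%, or 84 (42 per arm), are expected "to participate in their assigned condition and be included in the RCT".

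The Randomization paragraph opens with "Persons meeting eligibility criteria will be randomized to ROST or the ECC" and continues: "This procedure will repeat until 7, six-member ROST groups and 7, six-member ECC groups are assembled". Smaller groups are allowed if recruitment is slow.

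The power claim in Data Analyses is: "A sample of 84 subjects who participate in their study condition after randomization should provide power of .8", for d=.8 or above at two-tailed p<.05. The same paragraph says that individuals' "observations cannot be assumed independent", and it plans multilevel growth models with baseline adjustment. It calls the analysis intent-to-treat because "all subjects undergoing randomization will be included", with multiple imputation and pattern-mixture models for missing data.

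**The concern.** Three planning figures do not connect.

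- **Screening.** The first step of the forecast does not give the number printed beside it, so the planned screening load is uncertain.
- **Power.** The inputs printed with the power claim give a clearly different value under the simplest calculation. The inputs that might explain the difference are not stated.
- **Population.** Power is stated for those who participate, but the analysis is of those randomized. The two differ by 103 − 84 = 19 people (18% of 103). People who do not take up their condition may dilute the treatment effect.

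At stake is whether a reader can tell what effect the planned analysis is able to detect. As written, that cannot be done.

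**Working it through.** **1. Recruitment forecast** (inputs from Enrollment and Participants)

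- First step: 177 × .80 = 141.6, against 160 stated.
- Later steps: 160 × .80 = 128; 128 × .80 = 102.4 (stated 103); 103 × .82 = 84.5 (stated 84). These hold within rounding.
- Rate needed to reach 160 from 177: 160/177 = .904. Number needed at 80%: 160/.80 = 200.
- Keeping 177 and all stated rates: 141.6 → 113.3 → 90.6 → 74.3.

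**2. The stated power** (inputs from Data Analyses: 42 per arm, d=.8, two-sided .05)

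Method: noncentral t with noncentrality d/SE, in units of the outcome SD.

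- Independent observations: SE = √(2/42) = .218; noncentrality .8/.218 = 3.67; 82 df; power **.95**. Detectable d at power .8 is **.62**.
- Other readings do not give .8 either: one-sided .05 gives .98, two-sided .025 gives .91, and two-sided .01 gives .845.
- Under independence, d=.8 needs only about 26 per arm (power .807; 25 per arm gives .791).

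Which clustering assumption would give .8? Take seven groups of six per clustered arm, no missing data and no baseline gain. The ICC and the df are assumptions, because the documents give neither.

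- Both arms clustered: variance 2 × (1 + 5 × ICC)/42.
- ROST only: variance [(1 + 5 × ICC) + 1]/42.

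| Clustered arms | df | Power at ICC .05 / .10 / .15 / .20 | ICC at which power is .8 |
|---|---|---|---|
| Both | 12 | .85 / .785 / .72 / .66 | .09 |
| Both | 82 | .90 / .84 / .78 / .73 | .13 |
| ROST only | Satterthwaite | .90 / .87 / .83 / .79 | .19 |
| ROST only | 82 | – | .27 |

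The ICC that would explain .8 therefore varies threefold with choices the plan does not state. Which arms are clustered is itself unclear. The Control Arm paragraph describes a workbook, resource guides and referrals but no group sessions, whereas the Randomization paragraph assembles control groups of six.

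Baseline adjustment works the other way. With an assumed correlation of .5 the variance is multiplied by 1 − .25 = .75. At ICC .10, power for 84 then rises from .785 to .89 (both arms, 12 df) and from .87 to .94 (ROST only, Satterthwaite df).

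**3. Power for the population to be analysed** (103 randomized, 51.5 per arm)

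- Seven groups per arm give a mean size of 51.5/7 = 7.36. At ICC .10 the design effect is 1 + 6.36 × .10 = 1.64.
- Lower bound for dilution, if non-participants gain nothing: d = .8 × 84/103 = .652.

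| 103 randomized, none missing, no baseline gain | d=.8 | d=.652 |
|---|---|---|
| Independent | .98 | .91 |
| ICC .10, both arms, 12 df | .83 | .66 |
| ICC .10, ROST only, Satterthwaite df | .91 | .77 |

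All figures are for a comparison at a single time point. The planned growth model may differ somewhat.

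**The case against.** **The .8 may be deliberate.** The plan rejects independence, so .95 is not the right benchmark, and a claim of .8 is not contradicted by a higher figure under independence. The number could hold a clustering allowance, or one for missing data: 52 analysed of 84 would be 1 − 52/84 = 38% missing. This stands as an explanation. It does not close the gap, because no such allowance is written down and the one implied depends heavily on unstated choices.

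**A reader might infer that the trial is underpowered.** The documents do not support that. Under independence, power exceeds .8 for 84 and for 103 even with the lower-bound dilution (.84 for 84, with d = .8 × .82 = .656; .91 for 103). It falls below .8 only under some assumed combinations of clustering and dilution, and baseline adjustment would recover part of that.

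**A reader might infer a planned exclusion of 19 randomized people.** The recruitment wording invites this, but that paragraph is a forecast. Data Analyses defines the analysis set as all randomized, and the Follow-up interviews paragraph plans post-treatment and 3-month interviews for everyone who completed baseline. The phrase is loose wording, not an exclusion rule.

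**A reader might infer that all 128 eligible people are randomized.** That conflicts with the explicit 80% attendance step. The only count given for attending randomization is 103. The 14 groups of six (14 × 6 = 84) can be read as groups of those who participate, but the text does not say so.

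**It is a pilot.** True, and this limits the severity. The plan nevertheless makes a formal power claim tied to a significance level.

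**Conclusion.** The point holds as a fault in the planning figures, worth fixing, and not as a finding against the trial's size.

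- **Certain:** 80% of 177 is 142, not 160. Because randomization repeats until groups are filled, the effect falls on the planned screening load and not necessarily on the final sample.
- **Certain:** 84 participants at d=.8 and two-sided .05 do not give .8 without a further assumption, and none is stated. Whether .8 is right for the planned model cannot be determined.
- **Certain:** power is stated for 84 participants, whereas the analysis is of all randomized, 103 on the protocol's count.
- **Dependent on assumptions:** at ICC .10, power for 103 runs from .66 (both arms clustered, full dilution, no baseline gain) to .91 (ROST only, no dilution). The ICC, the clustered arms, the dilution and the absence of missing data are assumptions made here to show the range.

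**What to change.** 1. **Enrollment and Participants.** Change the rate to about 90%, or the number screened to 200, or carry the lower counts through, whichever the authors intend. Delete the phrase "to participate in their assigned condition and be included in the RCT" as far as it speaks of inclusion, keeping only the forecast of participation.
2. **Randomization.** Reconcile 14 groups of six with 103 randomized. Say whether the groups count those randomized or those who participate, and whether control participants actually meet in groups.
3. **Data Analyses.** Replace the power sentence with one for the intent-to-treat, clustered analysis of the randomized number. State the ICC range, clustered arms, df method, baseline correlation, missing-data rate and any dilution from non-participation. Possible wording, with the authors' own values in place of those assumed here: *With 103 randomized in seven groups per arm, no missing outcomes, no gain from baseline adjustment and two-sided .05, power for d=.8 is .98 if outcomes are independent and, at ICC .10, .83 with both arms clustered (12 df) or .91 with ROST only (Satterthwaite df). If non-participants gain nothing (d=.652), the figures are .91, .66 and .77.* Further rows should show the expected missing-data rate and baseline correlation.

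**Cost.** Text and a short calculation. No added randomized participants, no extra visits and no change of analysis. If 200 is the true screening number, the planned count rises by 23. The only downside is that the restated power may look less favourable than .8 under some assumptions.
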